6.5 Liver Function Tests

If subjects demonstrate an increase in AST, ALT or total bilirubin (TB) greater than 2 times their baseline values (mean of Screening & Visit 1), there should be repeat tests of transaminases (AST and ALT), bilirubin, and physical exam performed within 48-72 hours. If the levels then decrease, the subjects will be under close observation (repeat testing 2-3x weekly) until the levels return toward the individual's baseline values. Should these levels continue to be elevated, the drug should be discontinued.

Subjects should be discontinued for elevations of transaminases (AST or ALT) or TB above baseline associated with symptoms of right upper quadrant abdominal pain, fatigue, anorexia, nausea or vomiting, or eosinophilia. Subjects should be discontinued for persistent (> 1 month) increases of AST and ALT and/or TB > 2 times baseline.

Subjects may be rechallenged with study drug and closely monitored with repeat testing at least weekly. Re-elevation of values after re-challenge necessitate permanent discontinuation of study drug (but continuation of study visits).

If a new concomitant medication with known hepatotoxicity is started and liver function tests rise to meet the above criteria, the known hepatotoxin should be discontinued (replaced) if possible and liver function tests be followed in the same manner as outlined above. If liver function tests remain elevated or increase further, then the study drug should be discontinued (and subjects should continue with the study visits).

6.6 PT/INR Tests

If subjects demonstrate an increase in PT or INR > 2 times the baseline value (mean of Screening & Visit 1), repeat tests of PT or INR and eosinophil counts should be performed within approximately 48-72 hours. If the PT or INR elevation is associated with changes in liver biochemistries, the subject should be followed closely per Investigator judgement with repeat testing at least weekly until levels return toward baseline values. Subjects should be discontinued

from study drug (and continue with study visits) and be referred for treatment if they show signs of spontaneous, serious or persistent bleeding.

7 STUDY PROCEDURES AND EVALUATIONS

7.1 Vital Signs

Vital signs will be measured at every study visit including Screening and Follow-Up visits . Vital sign measurements will include blood pressure and heart rate, will be taken pre-dose.

For all subjects, oral temperature (in degrees Celsius) will be measured at Screening and pre-dose on Day 1 (Study Visit 1) and at the Follow-up visit on Day 374 (Study Visit 8).

7.2 Physical Examinations

A complete physical examination will be performed at Screening and at the Follow-Up Visit (Day 374, Study Visit 8); a limited physical examination will be performed at all other study visits (Study Visits 1-7). Information regarding body weight, waist circumference and assessment for the presence of edema will be collected at all study visits and height will be recorded only at Screening. Subjects are to be weighed in similar attire without shoes on the same scale at each visit. Measure waist circumference as follows:

Locate the lowest rib and the iliac crest. Place the tape measure evenly around the bare abdomen at the midpoint between the lowest rib and the iliac crest. Read the tape measure and record the waist circumference in centimeters.

The complete physical examination will be comprised of the following general categories of parameters: General Appearance, Dermatological, Head Ears Eyes Nose and Throat (HEENT)/Neck, Pulmonary, Cardiovascular, Gastro-Intestinal, Neurological, Extremities, Lymphatic, and Other.

The limited physical examination will be comprised of at least the following categories of parameters: Pulmonary, Cardiovascular, and Extremities. The presence or absence of edema will be recorded as “yes“ or “no“ at each complete and limited physical examination. If “yes,“ a grade will be recorded for the edema. Peripheral edema will be assessed as follows:

Place your index finger over the participant's tibia, 10 cm above the lateral malleolus. Exert pressure for 5 seconds. Any depression that does not resume its original contour almost immediately is a sign of pitting edema. Record if there is no edema observed. The following scale should be used to grade any edema that is observed.

Grade **Physical Characteristics**

- 1+ No visible change in shape of the extremity, pitting \leq 2 mm, pit disappears rapidly
- 2+ No marked change in the shape of the extremity, 2 mm < pitting \leq 5 mm, pit usually disappears in 10-15 seconds
- 3+ Noticeably swollen extremity, 5 mm < pitting \leq 10 mm, pit may persist for about a minute
- 4+ Very swollen and distorted extremity, very deep pit > 10 mm, pit may persist 2 - 5 minutes

7.3 Electrocardiograms

Twelve-lead ECGs will be performed at Screening, Study Visit 5 (Day 180), Visit 7 (Day 360) and Visit 8 (Day 374). The ECG obtained at the Screening visit will serve as the baseline measurement. All scheduled ECGs will be performed after the subject has rested quietly for at least 10 minutes in a supine position. The QT correction derived by the ECG machine or computed manually should be recorded.

To ensure safety of the subjects, a qualified individual at the Investigator site will make comparisons with baseline measurements. If the QTc is >60 msec from the baseline; or an absolute QTc value is >500 msec for any scheduled ECG, the ECG will be repeated 2 more times, approximately 2-4 minutes apart.

If a machine-read QTc value is prolonged, as defined above, repeat measurements may not be necessary if a qualified physician's interpretation determines that the QTc values are in the acceptable range.

In some cases, it may be appropriate to repeat abnormal ECGs to rule out improper lead placement as contributing to the ECG abnormality such as readings of ischemia, T wave changes, or infarct.

7.4 Laboratory Assessments

For all subjects, blood samples for safety laboratory assessments will be drawn at every visit (Table 1). All blood samples for clinical chemistry and hematology should be drawn in a fasted state (approximately 10 hours). A certified central clinical laboratory will be used to perform all routine hematology, clinical chemistry and urinalysis. Table 2 provides a summary of safety laboratory tests performed during the study.

All clinical laboratory tests will be performed by the central laboratory specified in Form FDA 1572 Section 4. The central laboratory reference ranges will be used. Eligibility at screening will be based on central laboratory assessments.

Local laboratory assessments may be used to manage patient care during the conduct of the study (eg, routine care, unscheduled visits, urgent care). Such laboratory data will not be entered into the study database and local laboratories will not be included on the FDA 1572 form.

Table 2. Safety Laboratory Tests

Hematology	Chemistry	Urinalysis	Other
Hemoglobin	Albumin	Bilirubin, Blood	
Hematocrit	Alkaline phosphatase	Glucose, Ketones, pH, creatinine,	
Platelets, RBC with indices	ALT, AST, BUN, Bicarbonate	Protein, Specific gravity	Pregnancy test ^{b,c} FSH ^{b,c}
WBC with differential	Calcium, Chloride, Creatinine, Fasting Plasma Glucose, Fasting Insulin, FFA	Microscopic exam ^a	hsCRP CK-18 [M30 & M65] HMW adiponectin osteocalcin Serum CTX TIMP-1 PIIINP HA Pro-C3
HbA1c	LDH, Phosphorus		
INR, PT	Potassium, Sodium Gamma-glutamyl transpeptidase Total Bilirubin Total Protein, Uric acid Cholesterol (total, HDL, LDL, VLDL) Triglycerides		

^a Only if positive for blood or protein

^b Only at Screening (β-hCG), Day 1 (urine dipstick), and Day 374 (urine dipstick)

^c Females only.

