6.4 Type 2 Diabetes Mellitus

Refer to subject's healthcare provider for diabetic care; however, note that no change in dose is allowed for GLP1 agonists or SGLT2 inhibitors during the study and these drugs cannot be added as rescue medications during the study if the subject had not been on a previous stable dose of either drug 3 months prior to randomization. Use of PPAR γ agonists (pioglitazone or rosiglitazone) or insulin are prohibited during the study.

Subjects being treated with therapeutic agents for diabetes should be on stable dose(s) of the following antidiabetic medications at least 3 months prior to randomization and for the full duration of the trial: metformin, GLP1 agonists, SGLT2 inhibitors, sulfonylureas and DPP4 inhibitors.

If, during the study, a measurement of HbA1c exceeds 9.5% at two consecutive visits, the following suggested rescue approach may be followed:

1. Start metformin or up-titrate metformin if the subject is already taking it

2. Start a DPP4 inhibitor or uptitrate the DPP4 inhibitor if the subject is already taking a DPP4 inhibitor
3. Start careful titration of a sulfonylurea or titrate sulfonylurea if the subject is already taking it.

If no reversible cause is identified or hyperglycemia persists despite counseling and all permitted co-therapies, subject should be discontinued from study drug, referred for treatment, and continue in the study and complete the required study visits.

If a measurement of fasting plasma glucose (FPG) during the study is lower than 60 mg/dL, an alert will be sent to the investigational site and confirmatory FPG should be performed at the site within 7 days. In case of a symptomatic hypoglycemic event and if the subject is on a sulfonylurea, the sulfonylurea dose should be reduced by 50% or discontinued. Severe hypoglycemia is defined as any hypoglycemia requiring the assistance of a third party, hospitalization or associated with seizures or coma. Refer to [Section 9](#) Adverse Events for reporting instructions.

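### Repeat liver tests that decide whether study drug is stopped may be run locally and so kept out of the database, and the SAP has no worst-value summary

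*Protocol*

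**What the plan says.** Protocol 7.4 sets the default: "All clinical laboratory tests will be performed by the central laboratory specified in Form FDA 1572 Section 4". It then gives a permission: "Local laboratory assessments may be used to manage patient care during the conduct of the study (eg, routine care, unscheduled visits, urgent care"). The next sentence excludes the results: "Such laboratory data will not be entered into the study database and local laboratories will not be included on the FDA 1572 form". No exception follows for tests that the protocol itself demands.

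Protocol 6.5 demands such tests. When AST, ALT or total bilirubin exceeds twice baseline, "there should be repeat tests of transaminases (AST and ALT), bilirubin, and physical exam performed within 48-72 hours". If levels then fall, "the subjects will be under close observation (repeat testing 2-3x weekly) until the levels return toward the individual's baseline values". If they do not, "Should these levels continue to be elevated, the drug should be discontinued". The section also stops drug for elevations lasting more than one month, and permanently for re-elevation after re-challenge, during which testing is at least weekly. It does not name the laboratory.

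Protocol 6.6 has a parallel repeat rule for PT/INR: "repeat tests of PT or INR and eosinophil counts should be performed within approximately 48-72 hours". It too names no laboratory.

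SAP 7.9.2 presents laboratory data by visit. SAP 6.1 assigns unscheduled values to visit windows but uses the scheduled value when both exist, except at baseline. SAP 7.1 lists all collected data.

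**The concern.** The liver rule acts on repeat values, and those repeats are by nature unscheduled. That is one of the settings in which 7.4 permits local testing and then bars the result from the database. The protocol leaves the choice to each of about 50 to 75 sites, so completeness of the liver data could differ by site.

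At stake is the ability to judge hepatic safety, in patients with liver disease, from the trial's own data. The questions are whether a rise was confirmed, how high it went, whether bilirubin moved with it, whether it resolved, and whether it came back on re-challenge. If the repeats are local, the answers sit only in site source documents.

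**Working it through.** The plan states no figure to reproduce. The check sets the sections side by side, with simple arithmetic on the visit schedule.

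**1. Can a required repeat coincide with a scheduled visit?** Visits fall on Days 1, 30, 60, 90, 180, 270, 360 and 374 (Protocol 6.1). Windows are ±7 days for Visits 2 to 7 and ±3 days for Visit 8 (Protocol Table 1).
- Nominal gaps: 29, 30, 30, 90, 90, 90 and 14 days.
- Smallest possible gap: Visit 7 late to Visit 8 early, (374 − 3) − (360 + 7) = 4 days.
- Largest possible gap: 90 + 7 + 7 = 104 days.
- The repeat is due in 48 to 72 hours, that is 2 to 3 days.

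Since 3 < 4, a repeat triggered at a scheduled visit and done on time always falls before the next scheduled visit. It is an unscheduled test.

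**2. Which repeat values decide what?**

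| Rule | Study-drug stop depends on repeat laboratory values? |
|---|---|
| 6.5 liver | Yes: continued elevation, persistence beyond one month, re-elevation after re-challenge |
| 6.6 PT/INR | No: signs of bleeding |
| 6.4 low glucose | No study-drug stop; the action concerns the sulfonylurea after a symptomatic event |

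Only the liver rule carries the concern in full. PT/INR and eosinophil results matter as accompanying evidence; 6.5 itself names eosinophilia.

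**3. Share of repeats missing.** Let p be the proportion of 6.5 repeats run locally. Under 7.4 as written, the missing share equals p. The documents do not give p, so the range is 0% (all central) to 100% (all local).

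**4. Do other records recover the values?**
- *Adverse events (Protocol 9.1 and 9.1.1).* An abnormality needing intervention or investigation beyond a repeat test is reportable, with severity, duration and outcome. That records an event, not a series of values. Abnormalities tied to a clinical event are directed to source documents.
- *Discontinuation (SAP 7.2 and 7.9.1).* Reasons for stopping, and adverse events leading to it, are tabulated. No values are attached.
- *Adjudicated liver events (SAP 7.9.6).* These are ascites, encephalopathy, variceal bleeding, HCC and transplant. Enzyme and bilirubin rises are not included.

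**5. Would central repeats be visible?** They would be listed (SAP 7.1). For a parameter measured at all visits, the SAP 6.1 windows cover every day from Day 2 onward without a break. An unscheduled post-baseline value therefore enters a by-visit table only when the scheduled value for that window is missing. Example: a trigger at Day 180, with repeats on Day 183 and later. The Month 6 window is Days 136 to 225, so the Day 180 value represents all of it, and a higher value on Day 183 appears in listings only.

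**6. Would the abnormality table show it?** SAP 7.9.2 flags ALT and AST by visit at a ratio to baseline of at least 5. The 6.5 rule starts above 2. A stop on transaminases between 2 and 5 times baseline is not flagged there. For bilirubin the flag is at least 2, so this mismatch does not arise. No table gives a worst on-treatment value.

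**The case against.** The strongest reply is that central testing is the stated rule for all clinical laboratory tests, and local testing is only a permission for patient care. Repeats under 6.5 are protocol-specified, so they may be meant to go centrally, and laboratory manuals not available here may say so. A trigger found at a scheduled visit is already a central value in the database. The SAP accepts unscheduled values, and the event and the stop would normally be recorded. Using one laboratory with one set of reference ranges is a defensible choice.

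Most of this stands, and it limits the point to a possible loss. It does not close the gap, because 7.4 names unscheduled visits among the local uses, excludes those results outright, and makes no exception for 6.5.

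Three stronger readings are tempting and not supported:
- *The confirmatory values will be lost.* This assumes every repeat is local, which the documents do not say.
- *The PT/INR and low-glucose rules are equally affected.* Neither stops study drug on a repeat laboratory value. The glucose instruction, "confirmatory FPG should be performed at the site within 7 days", need not mean a local assay, since central samples are also drawn at sites.
- *A typical number of tests is lost per episode.* Multiplying two to three tests weekly by one month joins two separate provisions: the frequency applies once levels are falling, and the month is the persistence criterion. The documents give neither episode length nor frequency.

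**Conclusion.** The point holds for the liver rule. Protocol 7.4 allows the values behind a 6.5 stopping or re-challenge decision to be absent from the study database, and nothing in 6.5 prevents it. The missing share of repeats is 0% to 100%, depending on an unstated local/central split. Only subjects who trigger the rule are affected, and their number is not given. The most exposed case is a rise first found in a local sample between visits after Month 3, when scheduled tests are nominally 90 days apart and at most 104.

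Separately, and whichever laboratory is used, the by-visit tables can omit the peak because the scheduled value takes precedence and no worst-value summary exists. That part follows from SAP 6.1 and 7.9.2 alone and needs no assumption about where tests are run.

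This is a gap in data capture and reporting. It does not call any clinical threshold into question, and it does not touch the primary efficacy analysis.

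**What to change.** **Protocol 7.4.** State that repeats done under 6.5, with any accompanying PT/INR and eosinophil results under 6.6, are sent to the central laboratory. Where a local laboratory is used, the results are entered on an unscheduled-laboratory eCRF page with date, unit and local reference range.

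**SAP 7.9.2.** Add a summary by treatment group of the worst on-treatment ALT, AST and total bilirubin that includes unscheduled values. Define its period explicitly; the safety set's limit of 14 days past the last dose (SAP 5.3) is the natural choice. Flag local results and show them as multiples of the local ULN. ULN scaling does not repair a local value divided by a central baseline, so ratios to baseline should use central values only or be flagged as cross-laboratory.

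**Cost.** One eCRF page, one summary table, and data entry for subjects who trigger the rule. The downside is some between-laboratory heterogeneity in the flagged values. No threshold, testing frequency or stopping rule changes.

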7.5 Efficacy and Pharmacokinetic Assessments

For all subjects, blood samples for pharmacologic (efficacy and safety) assessments will be drawn at all visits except Screening (Table 1). All blood samples should be drawn in a fasted state (approximately 10 hours). Instructions for collecting, processing, storing and shipping of blood samples for pharmacologic and pharmacokinetic analyses will be provided in the Laboratory Manual.

Blood samples for trough PK analysis of MSDC-0602 and MSDC-0597 will be collected pre-dose at Study Visits 2, 4, 5, 6 and 7 (Days 30, 90, 180, 270 and 360).

Blood samples for analysis of FPG and HbA1c will be collected at Screening.

Blood samples for analysis of insulin, HOMA-IR, FPG, HbA1c, TG, FFA and fasting cholesterol (total, HDL, LDL, VLDL) will be collected as part of the standard chemistry profile at Study Visits 1, 5, and 7 (Days 1, 180 and 360).

Blood samples for analysis of liver function tests (AST, ALT, bilirubin, PT/INR, ALP, GGT and albumin) will be collected at Study Visits 1, 2, 3, 4, 5, 6 and 7 (Days 1, 30, 60, 90, 180, 270 and 360).

Blood samples for analysis of HMW adiponectin, hsCRP, osteocalcin, serum CTX concentrations will be collected at Study Visits 1, 5, and 7 (Days 1, 180, and 360).

Blood samples for biomarkers of liver apoptosis (CK-18 [M30 and M65]) will be collected at Visits 1, 5 and 7 (Days 1, 180, and 360), whereas blood samples for TIMP-1, PIIINP, HA will be collected at Visits 1 and 7 (Days 1 and 360).

Serum samples for NMR analysis of lipoprotein particle size will be collected at Study Visits 1 and 7 (Days 1 and 360).

Blood samples will be collected at Visit 1 (Day 1) to be analyzed for genotyping.

Plasma samples for future miRNA measurements and additional biomarkers of interest will be collected at Study Visits 1, 5 and 7 (Days 1, 180 and 360).

Data obtained from the circulating liver function tests and other biomarkers will be used to calculate composite scores that may provide an indirect measure of changes in fibrosis from baseline to the 12 month endpoint (Days 1 and 360).

It is estimated that approximately 226 mL of blood for the safety, pharmacokinetic, and pharmacodynamic parameters will be drawn from each subject who completes the trial.

7.6 Transient elastography (FibroScan) measurement of liver fibrosis

Vibration-Controlled Transient Elastography or FibroScan is a non-invasive methodology that assesses liver fibrosis/steatosis by measuring liver stiffness using ultrasonographic elastometry. The measures are expressed in kilopascals (kPa) and db/m, and values increase with greater fibrosis/steatosis. FibroScan will be conducted at Days 1 and 360 using M or XL probe as

needed. Averages of ten measurements for kPa and CAP scores will be recorded as suggested by the manufacturer for the baseline and end of study measurements. FibroScan values of CAP \geq 270 db/m and kPa \geq 8.5 will be used to qualify subjects for liver biopsy if no historical liver biopsy is available.

7.7 Liver Biopsies

All subjects will have a liver biopsy at screening/baseline and at Visit 7. Qualifying liver biopsy must be within 9 months prior to Screening. If no usable liver biopsy is available within 9 months prior to Screening, a liver biopsy must be performed during Screening after the following criteria are confirmed:

- a. AST \geq 20 U/L
- b. FibroScan with CAP score \geq 270 db/m and kPa \geq 8.5

The primary clinical diagnosis to enter the study will be performed by a central clinical pathologist. Slides/paraffin blocks will be shipped to the central laboratory where slides will be digitized using a Scanscope™ XT (Aperio Technologies, Inc.) ultra-fast, high-capacity slide scanner. Digitized slides will be sent to a single expert histopathologist who is a member of the NASH Clinical Research Network. The expert pathologist reader will provide individual scores for both NAS components and fibrosis scores.

At the completion of the study, the liver biopsy slides at Visit 7 will be used for diagnosis by the local pathologist and then scanned, digitized and sent for blinded reading by the expert histopathologist.

Before performing a percutaneous liver biopsy, there must be a clearly defined indication for the biopsy, and the risks to the subject should not outweigh the potential benefits.

The subject's platelet count and PT (or INR) may be checked prior to the liver biopsy according to local standards. Local guidelines and thresholds for hemostatic parameters should be used as they are in everyday clinical practice. Usually a platelet count $>$ 60,000/ μ L, a PT $>$ 60% or longer by no more than 4 seconds over the control or INR $<$ 1.3, and a normal bleeding time are acceptable for performing percutaneous liver biopsy in a subject that has stopped taking any antiaggregant therapy for $>$ 5 days. If these conditions are not all respected, a safer option would be to perform the liver biopsy by trans-jugular route, when available.

Sedation is recommended to be given for percutaneous liver biopsy, and should be given with caution in liver disease.

The recommended biopsy procedure to be applied is:

- Needle core biopsy
- Biopsy obtained with a 16 or lower gauge needle
- A tissue core \geq 2 cm long (\geq 10 portal tracts) represents optimal biopsy length

- Preferably obtain biopsy from the right lobe. If left lobe biopsy is used for inclusion, a left lobe biopsy should be used for future biopsies.

Post-biopsy observation: It is recommended that the subject should remain in the hospital consistent with the standard of care of that institution.

The biopsies will be sent to the central laboratory and then to a central reader who will read the biopsies to determine the eligibility to the study according to the fibrosis stage and consistency with NASH diagnosis. Biopsy slides will be blinded for subject and visit identification prior to central reading.

